HRP-503B – BIOMEDICAL RESEARCH PROTOCOL
(2016-1)

Protocol Title: Impact of cigarette and e-cigarette flavors on adult smoking behavior

Principal Investigator: [name].

Version Date: 4/18/2019

(If applicable) Clinicaltrials.gov Registration #: NCT04009850

INSTRUCTIONS

This template is intended to help investigators prepare a protocol that includes all of the necessary information needed by the IRB to determine whether a study meets approval criteria. **Read the following instructions before proceeding:**

1. Use this protocol template for a PI initiated study that includes direct interactions with research subjects. Additional templates for other types of research protocols are available in the system Library.
2. If a section or question does not apply to your research study, type “Not Applicable” underneath.
3. Once completed, upload your protocol in the “Basic Information” screen in IRES IRB system.

SECTION I: RESEARCH PLAN

1. **Statement of Purpose:** State the scientific aim(s) of the study, or the hypotheses to be tested.

The purpose of this project is to understand how menthol flavors in tobacco products influences tobacco use behavior among current adult cigarette smokers. This project uses the same procedures that were already approved in an earlier protocol, HIC# 2000020334. **“Impact of Switching to Non-Menthol Cigarettes Among Smokers”**

The FDA has proposed to ban characterizing menthol flavor in combustible products only, but not e-cigarettes, so research is needed to understand how the availability of menthol flavor in e-cigarettes influences the likelihood that an adult cigarette smoker will switch from combustible cigarettes to a potentially less-harmful e-cigarette product.

In this pilot of 50 non-treatment-seeking adult smokers, we will investigate within-person changes in smoking behavior when current menthol smokers are switched to non-menthol cigarettes for 4 weeks to model the effects of the ban of menthol flavor in cigarettes. Additionally, participants will be randomized to receive either 1) a tobacco flavored non-menthol e-cigarette (N=25) or 2) a menthol flavored e-cigarette (N=25) to use for the 4 weeks. Outcomes will assess in-vivo cigarette and e-cigarette use, biomarkers of tobacco and menthol exposure, nicotine dependence, quitting motivation and confidence, and product satisfaction and willingness to continue to use the alternative products.

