We will evaluate within-subject changes in cigarette satisfaction and smoking behavior after switching from menthol cigarettes. We will assess within-person changes in cigarette satisfaction and smoking behavior during the last week of the non-menthol cigarette smoking period compared to the menthol cigarette smoking period. Given that menthol cigarettes are especially reinforcing to menthol-preferring smokers due both to sensory and pharmacological effects, we expect that switching to a non-menthol cigarette will be less reinforcing and result in a) fewer cigarettes smoked per day, b) lower biomarkers of nicotine exposure (e.g., cotinine, TNE), c) lower nicotine dependence, d) lower ratings of satisfaction, liking, craving, e) greater motivation and confidence quitting smoking.

We will investigate whether outcomes differ between subjects based on use of menthol vs. tobacco flavored e-cigarettes. We will compare preference and use of both the cigarette and e-cigarette products during the switching period. We will evaluate the extent to which menthol flavored (vs. tobacco flavored) e-cigarettes are preferred among menthol smokers and whether changes in cigarette smoking outcomes differ by e-cigarette flavor condition.

2. **Probable Duration of Project:** State the expected duration of the project, including all follow-up and data analysis activities.

2 years. We anticipate recruiting and enrolling 50 subjects over 1-1.5 years and will complete data entry and analysis by the end of 2 years.

3. **Background:** Describe the background information that led to the plan for this project. Provide references to support the expectation of obtaining useful scientific data.

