The FDA recently announced a plan to advance a Notice of Proposed Rulemaking to ban menthol in combustible tobacco products, including cigarettes, but not e-cigarettes¹⁴. However, empirical evidence is needed to understand the potential impact on smoking behavior among current menthol smokers if menthol additives were banned in cigarette products. An earlier approved protocol, HIC# 2000020334 evaluated the extent to which switching current menthol smokers to non-menthol cigarettes changes smoking behavior to model the potential impact of the ban of characterizing menthol flavor in cigarettes.

There is evidence that many adult cigarette smokers use e-cigarettes^{15,16}, and that using e-cigarettes can be an effective way for adult smokers to reduce their combustible cigarette use^{15,17}, even more effective than other nicotine replacement approaches¹⁷. Thus, the current proposal aims to evaluate how e-cigarette flavor availability influences combustible cigarette smoking, specifically by investigating the extent to which continued availability of menthol flavor in e-cigarette products will impact smoking behavior in the context of this proposed ban of menthol cigarettes.

4. **Research Plan:** Summarize the study design and research procedures using non-technical language that can be readily understood by someone outside the discipline. **Be sure to distinguish between standard of care vs. research procedures when applicable, and include any flowcharts of visits specifying their individual times and lengths.** Describe the setting in which the research will take place.

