Participants will return for visits at week 1, 2, 4, 6, and 10 (Figure 1). Consistent with our previously approved protocol, HIC# 2000020334, participants will smoke their own cigarettes during the baseline week, then will be provided with free menthol cigarettes of their own usual brand to smoke for one week (Phase I), and then will be switched to non-menthol cigarettes (Phase II). During phase II, participants will receive a JUUL e-cigarette. They will be randomized to either receive a tobacco-flavored e-cigarette (N=25) or menthol-flavored e-cigarette (N=25) to try for the 4-week period. Randomization will be stratified 1:1 by smoking heaviness (≤ 10 or > 10 cigarettes per day). Participants will receive instructions on how to use the e-cigarette and will be provided with refilled e-liquid cartridges for the 4-week period based on group assignment. The JUUL e-cigarette was chosen for this study because it is small, easy to use, is commercially available and is the most popular e-cigarette product, and is a closed system, meaning the device and e-liquids are not modifiable by the participant. We will monitor the participants' self-directed tobacco use behavior; they can choose to use or not use any of the tobacco products we provide. Participants will return for a follow-up visit at week 10 to evaluate smoking status and assess continued cigarette and e-cigarette use. At the end of the study, we will provide information on tobacco treatment programs to all participants.

Figure 1. Study timeline:

Screening Assessments: To screen for eligibility, participants will complete several assessments: 1) Cigarette preference questions assess current use of menthol cigarettes (i.e., “what brand of cigarettes do you prefer?” “what brand of cigarettes do you normally smoke?”). 2) Smoking history to assess smoking quantity and frequency such as number of cigarettes per day and number of years smoked. 3) Expired breath carbon monoxide (CO) measured in parts per million to confirm smoking status. 4) Drug use: to confirm participants are not currently using other substances (other than caffeine or nicotine) assessments will include i) a time-line follow-back interview to assess self-reported drug use quantity and frequency, ii) urine drug toxicology screens, and iii) current blood alcohol level measured with a breathalyzer.

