Visit Assessments: Eligible individuals will complete self-report assessments at baseline and research visits: 1) Nicotine dependence, measured by 1) Time to first cigarette in the morning as an index of smoking reinforcement^{18,19}, 2) Fagerstrom Test for Nicotine Dependence¹⁸ and Wisconsin Inventory of Smoking Dependence Motives^{20,21} to assess multiple dimensions of tobacco dependence such as automaticity, loss of control, and affective enhancement. Additional assessments include: 3) Questionnaire on Smoking Urges-brief²² to measure cigarette craving, 4) Wisconsin Smoking Withdrawal Scale²³, to assess 7 constructs of nicotine withdrawal: anger, anxiety, concentration, craving, hunger, sadness, and sleep and 5) Confidence and interest in quitting smoking, rated from 1 (not at all) to 10 (extremely), 6) measures of smoking behavior and cigarette reinforcement and satisfaction, 7) measures of behavioral economics using hypothetical purchase tasks to assess the reinforcing value and relative demand for the cigarette and e-cigarette products used in the study.

Biological Measures: Biomarkers of cigarette and menthol exposure will be collected at baseline and weekly research visits (baseline, visit 2, 4, 6, 10) to examine changes from baseline and to corroborate self-reported tobacco product use and menthol exposure during the trial. 1) Expired breath carbon monoxide (CO) measured in parts per million, 2) Urine cotinine to quantify nicotine exposure and metabolites, 3) Menthol glucuronide measured in the same urine sample as a marker of menthol exposure.

Adherence: Adherence to use of the cigarettes and e-cigarettes in Phase I (menthol cigarettes) and II (non-menthol cigarettes) – as described under procedures and in Figure 1 - will be closely monitored via subjective and objective measures. Participants will report the total number of cigarettes consumed each day and the total number of times the e-cigarette is used each day. Participants will be instructed how to save and return spent cigarette filters and e-liquid cartridges so the count can be verified by research staff, a procedure that has been utilized previously to verify adherence²⁴ and can further quantify use. We aim to restrict access to menthol

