 Decisionally Impaired	 Employees	 Pregnant women and/or fetuses
 Yale Students	 Females of childbearing potential	

NOTE: Is this research proposal designed to enroll children who are wards of the state as potential subjects?

Yes No

8. **Inclusion/Exclusion Criteria:** What are the criteria used to determine subject inclusion or exclusion?

Inclusion Criteria:

- (1) 18 or older
- (2) English literate
- (3) Smoke at least 5 cigarettes per day for the past 6 months
- (4) Expired breath carbon monoxide level $\geq 6\text{ppm}$ at baseline or detected urine cotinine level with NicAlert test strip
- (5) Report currently smoking menthol cigarettes
- (6) Report willingness to try an e-cigarette but not currently owning or using a device

Exclusion Criteria:

- (1) Seeking smoking cessation
- (2) Currently using any stop smoking treatments
- (3) History of serious psychiatric condition (i.e., bipolar disorder, schizophrenia)
- (4) Current uncontrolled medical condition
- (5) Current use of other substances (excluding nicotine and caffeine) or a positive urine toxicology screen
- (6) Living with a menthol smoker (to limit access to menthol cigarettes during the non-menthol phase of the trial)
- (7) Female participants will be excluded if they are currently pregnant (determined by a urine pregnancy test at intake) or breastfeeding or report an unwillingness to use effective birth control for the duration of the study

9. How will **eligibility** be determined, and by whom? Write here

Interested participants will call our office and will be provided with verbal information about the project. Interested participants will be initially screened by telephone and will provide their name and contact information and provide answers to short screening questions to assess age, smoking status, menthol preference, and to ensure they are not currently seeking smoking cessation treatment. Participants who meet initial eligibility screening will be invited to complete an intake session. At the intake session, participants will complete an informed consent form. Following this, a research assistant will obtain medical and substance use histories, urine drug and pregnancy tests, and breath CO levels. If study criteria are met, the participant will be scheduled for the subsequent sessions.

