10. **Risks:** Describe the reasonably foreseeable risks, including risks to subject privacy, discomforts, or inconveniences associated with subjects participating in the research.

We feel that this research poses minimal risks to the adults who are currently smoking cigarettes daily, have CO levels which verify this ($\geq 6\text{ppm}$), and report daily experience smoking tobacco cigarettes. We provide a detailed description of risks below.

Breath, and urine collections: Breath screening and urine collections should add no risks other than those normally associated with these procedures. Breath and urine screens will be performed by appropriately trained research staff during the screening and research visits.

Rating Scales and Assessments: These are all noninvasive and should add no risk. The major disadvantages are the time taken to complete them, and possible breach of confidentiality. We have done our best to make the assessment schedule in this study as brief as possible. Also, our past experience with these measures indicates that they are acceptable to subjects. Careful efforts aimed at maintaining confidentiality will be made, as described below.

Use of cigarettes/e-cigarettes: The requirement that participants be regular daily smokers who already use at least 5 cigarettes per day reduces the risk that a participant will experience an adverse reaction to the protocol. All smoking behavior will be self-directed by the participant in their normal every day environment. We will not ask participants to deliberately modify their smoking behavior in any way. We will only be monitoring the participants' self-directed tobacco use behavior; they can chose to use or not use any of the tobacco products we provide. We will inform participants about possible signs of too much nicotine exposure (e.g., nausea, vomiting, dizziness), similar to advice that is given to regular daily adult smokers who are trying a single or dual nicotine replacement therapy product. We will instruct participants to reduce their cigarette and/or e-cigarette use if they experience any of these symptoms. Smoking during pregnancy may be associated with increased risk for spontaneous abortion, increased perinatal mortality, and low infant birth weights. We will exclude females who are pregnant or nursing from this study. Finally, we will provide a list of smoking cessation resources to participants after they complete the study protocol.

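### The primary Phase I to Phase II change is credited to the non-menthol cigarette, but every participant is given an e-cigarette at the same switch, in a fixed order

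*Combined protocol and SAP*

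**What the plan says.** Section I.13 (Statistical Considerations) makes the within-person comparison of menthol and non-menthol phases the primary analysis. Section I.1 sets the window as the last week of the non-menthol period against the menthol period, and gives one reason for all five expected changes (a to e): "we expect that switching to a non-menthol cigarette will be less reinforcing and result in a) fewer cigarettes smoked per day". The same section describes menthol smokers being "switched to non-menthol cigarettes for 4 weeks to model the effects of the ban of menthol flavor in cigarettes". Section V (Potential Benefits) again states the purpose as finding out whether the switch to non-menthol cigarettes reduces reward, smoking and dependence, and lists the e-cigarette flavor question separately.

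The Procedures part of Section I.4 adds: "During phase II, participants will receive a JUUL e-cigarette". Only its flavor is randomised, 25 to menthol and 25 to tobacco. Inclusion criterion 6 (Section I.8) reads "Report willingness to try an e-cigarette but not currently owning or using a device". Section I.3 (Background) states that "using e-cigarettes can be an effective way for adult smokers to reduce their combustible cigarette use".

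A between-arm question is also planned: "whether changes in cigarette smoking outcomes differ by e-cigarette flavor condition". Section I.13 says that the pilot's effect sizes will inform the size of a larger study.

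**The concern.** At the start of Phase II three things change together for everyone. The cigarette loses its menthol, a new nicotine device with cartridges is supplied, and the participant moves later in a fixed sequence. Nobody stays on menthol cigarettes over the same weeks, and nobody smokes non-menthol cigarettes without an e-cigarette. The data therefore cannot say which of the three caused a change.

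The direction of the bias depends on the outcome. For cigarettes per day, the Background section itself says that e-cigarettes can reduce smoking, which is the direction of hypothesis a. For cotinine and TNE (hypothesis b), the device supplies nicotine and can hide a fall. The Risks section recognises the added exposure by warning of symptoms of excess nicotine and covering both products in that advice.

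Read as the hypotheses are worded, a fall in cigarettes per day would count as an effect of removing menthol, and an unchanged cotinine as its absence. Either could come from e-cigarette use or time. The same misreading could carry into the follow-up study through the effect size.

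**Working it through.** **What differs between the phases**

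| Feature | Phase I | Phase II | Varies between participants? |
|---|---|---|---|
| Cigarette | menthol, usual brand, free | non-menthol, matched brand, free | no |
| E-cigarette | none supplied; current users not eligible | JUUL with cartridges | flavor only |
| Calendar order | first | second | no |

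Free supply is the same in both phases, so it does not confound the contrast. The other three features change together. Neither arm isolates menthol removal: one still receives menthol through the device, and both receive a new source of nicotine. Adjusting for recorded e-cigarette use would not restore identification, because that use is self-chosen after the switch.

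**The plan's own figure.** Inputs from Section I.13: α=.05, d=.40 within-person, and β=.80, read as 80% power. The paired normal approximation, two-sided, is n = ((1.960+0.842)/0.40)² = 49.06, rounded up to 50. This matches the stated N. By the noncentral t, power at N=50 and d=.40 is 79.2%, and the detectable effect at 80% power is d=.404. The sample size is not in dispute.

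**How much a package effect could mislead.** The documents give no e-cigarette or time effect, so the shifts below are assumptions, in SDs of the within-person change. Power is from the noncentral t with 49 df and noncentrality d√50, two-sided .05.

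- *Menthol removal has no effect, and e-cigarette plus time lowers cigarettes per day by d.* For d=.2 the noncentrality is 1.41 and the test is significant 28% of the time. For d=.4 it is 2.83 and the figure is 79%.
- *Menthol removal lowers cotinine by d=.4, and e-cigarette nicotine offsets part of it.* With no offset, the chance of a significant fall is 79%. With an offset of .2 the net d is .4−.2=.2 and the chance is 28%. With an offset of .4 the net d is 0 and the chance is 2.5%.

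**Follow-up sizing (paired t, 80% power).** A pilot d of .40 implies 52 participants. Suppose the follow-up targets the cigarette effect alone:

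| Part of d=.40 due to the cigarette | n needed | Power with n=52 |
|---|---|---|
| .3 | 90 | 56% |
| .2 | 199 | 29% |

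**Precision of what can be estimated** (expected 95% half-widths, in SDs of change):

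- pooled change: 2.010/√50 = 0.28
- change within one arm: 2.064/√25 = 0.41
- difference between arms: 2.011×√(2/25) = 0.57

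The randomised comparison, 25 against 25, has 28% power at d=.40 and detects d of about .81 with 80% power.

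**The case against.** The strongest reply is that the package is the right target. Sections I.1 and I.3 describe a ban on menthol in combustible products that leaves e-cigarettes on the market, and non-menthol cigarettes with an e-cigarette to hand fits that scenario. This stands as far as it goes: the combined contrast is a relevant quantity. But hypotheses a to e are not worded as a package effect, and supplying a free device to every participant is not the same as a device being available for sale.

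Second, an earlier protocol studied the cigarette switch. It is cited here for procedures and background; no comparison with it is planned.

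Third, drift over time is limited. Participants are daily smokers with at least six months at five or more cigarettes per day, are not seeking to quit, and pass through a baseline week and a week of free menthol cigarettes first. These steps reduce drift but do not remove it, and they do nothing about the device.

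Fourth, the power figures show what would follow from an assumed bias, not that such a bias exists. That is right, and they should be read only that way. Likewise, if the follow-up study repeats the same package, the package effect size is the correct input and the 90 and 199 do not apply.

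Finally, the planned flavor comparison already requires change by arm, so a by-arm table adds little beyond making it explicit.

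**Conclusion.** The concern holds and should be fixed. The primary contrast identifies the joint effect of non-menthol cigarettes, a newly supplied e-cigarette and elapsed time, pooled over two flavors. The stated hypotheses credit it to the cigarette, and nothing in the analysis plan supports that step. The conclusion follows from the design and needs no assumed effect size.

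The likely size of the error is unknown. Under assumed shifts of 0.2 to 0.4 SD, the chance of a significant fall in cigarettes per day with no menthol-removal effect is 28% to 79%. The chance of detecting a true 0.4 SD fall in cotinine drops from 79% to between 28% and 2.5%. Bias is argued here for cigarettes per day and for cotinine/TNE; its direction for dependence, satisfaction and quitting motivation is left open.

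The randomised menthol versus tobacco e-cigarette comparison is unaffected, since both arms share the switch and the order, but it is imprecise. The sample size calculation stands.

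**What to change.** 1. In Sections I.1, I.13 and V, define the within-person contrast as the change after switching to non-menthol cigarettes with an e-cigarette supplied. Remove attribution to menthol removal alone. State that cigarette flavor, e-cigarette provision and time cannot be separated, and that bias can run in either direction.
2. Report the Phase I to Phase II change with its 95% confidence interval by randomised arm as well as pooled, and present neither arm as a clean menthol-removal estimate.
3. Limit randomised causal statements to the e-cigarette flavor comparison already planned, and state its precision: about 28% power at d=.40, and a detectable d of about .81.
4. State in Section I.13 that the within-person effect size passed to the follow-up study is that of the package.

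This costs wording and one small table, with no new participants, visits or assays. The price is a weaker headline claim for the within-person aim, by-arm intervals about 45% wider than the pooled one (0.413/0.284 = 1.45), and causal claims that rest on an imprecise comparison.

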Adverse events will be monitored for each subject participating in the study and attributed to the study procedures / design by [name] according to the following categories:

- a.) Definite: Adverse event is clearly related to investigational agent/participation.
- b.) Probable: Adverse event is likely related to investigational agent/participation.
- c.) Possible: Adverse event may be related to investigational agent/participation.
- d.) Unlikely: Adverse event is likely not to be related to the investigational agent/participation.
- e.) Unrelated: Adverse event is clearly not related to investigational agent/participation.

The following scale will be used in grading the severity of adverse events noted during the study:

- 1 Mild adverse event
- 2 Moderate adverse event
- 3 Severe unanticipated adverse event resulting in inpatient hospitalization or prolongation of existing hospitalization, a persistent or significant disability/incapacity, or a congenital anomaly/birth defect;
- 4 Life threatening event or
- 5 Fatal adverse event.

In addition to grading the adverse event, [name] and the study team will determine whether the adverse event meets the criteria for a Serious Adverse Event (SAE). An adverse event is considered serious if it:

- 1. is life-threatening
- 2. results in in-patient hospitalization or prolongation of existing hospitalization
- 3. results in persistent or significant disability or incapacity
- 4. results in a congenital anomaly or birth defect OR
- 5. results in death

6. based upon appropriate medical judgment, may jeopardize the subject's health and may require medical or surgical intervention to prevent one of the other outcomes listed in this definition, or
7. adversely affects the risk/benefit ratio of the study.

The study team, in consultation with the Yale TCORS Independent Data Safety Monitoring Board (DSMB), will evaluate the adverse event and determine whether the adverse event affects the Risk/Benefit ratio of the study and whether modifications to the protocol or consent form are needed. The DSMB includes experts in the field of tobacco use behaviors and challenge studies. The DSMB will review the study information and the plans for review prior to the initiation of the studies. They will provide an ongoing review every six months or more often if requested by the Board. The summary of the DSMB meeting will be submitted to the Yale HIC and to NIDA following each meeting.

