Subjects will be closely monitored for safety throughout the research trial. Although in our experience this is a very rare event, subjects who show significant deterioration (e.g., increased substance use or psychiatric symptoms, including significant suicidal or homicidal ideation), will be withdrawn from the study and referred for appropriate treatment.

At any point if the investigator feels that subjects' health or well-being may be threatened by continuation in the study, subjects will be withdrawn from the study. If participants have a medical emergency, they will be instructed to call 911. Subjects who experience a significant psychiatric or medical problem that requires overnight hospitalization at an acute care facility will be considered to have experienced an SAE.

The Principal Investigator, [name], will report the following types of adverse events to the Yale University Human Investigation Committee (HIC):

- a) serious AND unanticipated AND possibly, probably or definitely related events;
- b) anticipated adverse events occurring with a greater frequency than expected; and
- c) other unanticipated problems involving risks to subjects or others.

These adverse events or unanticipated problems involving risks to subjects or others will be reported to the Yale HIC within 5 days of it becoming known to [name]. The procedures for SAE reporting include written documentation using the clinical notes related to the adverse event and specific forms detailing the event with a sign-off by all appropriate supervisory personnel. Communication of recommendations and decisions from all parties (Yale Human Investigation Committee) will be made back to [name] in a timely manner.

- i. What provisions are in place for management of interim results?

The principal investigator is responsible for monitoring the data, assuring protocol compliance, and conducting the safety reviews at the specified frequency monthly. During the review process the principal investigator will evaluate whether the study should continue unchanged, require modification/amendment, or close to enrollment. The principal investigator and the Institutional Review Board (IRB) have the authority to stop or suspend the study or require modifications.

- ii. What will the multi-site process be for protocol modifications? N/A this is a single-site study

13. **Statistical Considerations:** Describe the statistical analyses that support the study design.

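### Severity grade 3 depends on expectedness and seriousness outcomes, so a severe, non-life-threatening event that is anticipated or lacks a listed outcome has no valid grade

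*Combined protocol and SAP*

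**What the plan says.** Section I, item 12 of the protocol (Data and Safety Monitoring Plan) gives five severity grades. Grade 1 is mild. Grade 2 is, in full, "2 Moderate adverse event". Grade 3 is "Severe unanticipated adverse event resulting in inpatient hospitalization or prolongation of existing hospitalization, a persistent or significant disability/incapacity, or a congenital anomaly/birth defect". The scale continues with "4 Life threatening event or" and a fatal event at grade 5. Only grade 3 mentions expectedness.

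The next step is introduced by "In addition to grading the adverse event": the team also decides whether the event is a serious adverse event (SAE), against seven criteria. Criterion 2 is that the event "results in in-patient hospitalization or prolongation of existing hospitalization". Criteria 3 and 4 are disability or incapacity, and congenital anomaly or birth defect. Later in the same item, a participant with a problem that "requires overnight hospitalization at an acute care facility will be considered to have experienced an SAE".

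Reporting to the HIC within 5 days has its own list. Trigger (a) is "serious AND unanticipated AND possibly, probably or definitely related events"; (b) covers anticipated events that are more frequent than expected; (c) covers other unanticipated problems.

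Section I, item 10 (Risks), on use of cigarettes and e-cigarettes, says: "We will inform participants about possible signs of too much nicotine exposure (e.g., nausea, vomiting, dizziness".

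**The concern.** Severity, seriousness and expectedness are three separate attributes of an adverse event. The plan largely treats them so: a scale for the first, a list for the second, and a reporting rule that uses the third. Grade 3 breaks the separation by making expectedness and three SAE outcomes conditions for calling an event severe.

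At stake is the accuracy of the recorded severity. The opening of item 12 accepts that anticipated events may occur and that events may be serious, yet the scale has no place for a severe anticipated event short of life-threatening. The gap touches the product risk that the protocol itself names, since participants are given both cigarettes and a nicotine e-cigarette in Phase II.

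**Working it through.** The plan states no figure on this point, so the check is a reading of the definitions against each other.

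**Step 1. Overlap with the SAE list.** Grade 3 outcomes are SAE criteria 2, 3 and 4. Grade 4 is criterion 1 and grade 5 is criterion 5. Every event that can be graded 3 or above is therefore already an SAE, and no grade above moderate rests on intensity alone.

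**Step 2. Severe events that are neither life-threatening nor fatal.** Cross expectedness (2 levels) with presence of a listed outcome (2 levels): 2 x 2 = 4 combinations.

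| Case | Unanticipated? | Listed outcome? | Grade 3 as written? | SAE? | Grade 3 if defined by intensity? |
|---|---|---|---|---|---|
| A | Yes | Yes | Yes | Yes | Yes |
| B | Yes | No | No | Only by criterion 6 or 7 | Yes |
| C | No | Yes | No | Yes | Yes |
| D | No | No | No | Only by criterion 6 or 7 | Yes |

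One combination in four reaches grade 3. B, C and D fail it, and they do not meet grade 4 or 5. What remains is mild, moderate or no grade. This counts logical cases, not events.

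**Step 3. The named nicotine signs.** Take severe vomiting or dizziness managed without admission, with no lasting disability. If it counts as anticipated because item 10 names the sign, it is case D. If its severe form counts as unanticipated, it is case B. Neither can be graded 3, so the result does not depend on how expectedness is judged.

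An admission for nicotine over-exposure is different. It is case A or case C, depending on a term the protocol does not define.

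**Step 4. Does the grade feed anything else?** The SAE criteria and HIC triggers (a) to (c) do not refer to it. Case C is an SAE whatever its grade. It fails trigger (a) because it is anticipated, and it meets trigger (b) only if its frequency exceeds an expectation that the protocol does not state. Regrading case C as 3 leaves both results unchanged.

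**The case against.** The strongest reply is that this is a drafting slip with little practical effect. Any hospitalised event is an SAE. Criterion 6 lets medical judgement capture a severe event without admission. The study team evaluates adverse events in consultation with the DSMB, which meets every six months or more often on request; the principal investigator reviews safety monthly; and SAE reports carry clinical notes and supervisory sign-off. Nothing says that any of these bodies sees grades alone. All of this stands, and it limits the consequence to the severity record. It does not supply the missing grade.

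Four stronger readings are tempting, and the documents do not support them.

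- A reader might infer that the grade 3 wording causes events to miss the 5-day report. The triggers do not use the grade. Any gap for anticipated SAEs comes from the wording of trigger (a) and the unstated expected frequency behind trigger (b), and rewording grade 3 would not close it.
- A reader might infer that every excluded event is recorded as grade 2. Grade 2 has no criteria and there is no default rule, so the strict reading is a gap; moderate is only the likeliest entry if the form demands one.
- A reader might infer that the protocol anticipates severe or hospitalised nicotine toxicity. Item 10 names signs such as nausea, vomiting and dizziness and goes no further.
- A reader might infer that a flavor difference in severe symptoms would be hidden. Item 13 (Statistical Considerations) plans no comparison of adverse events by arm.

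It can also be said that defining grade 3 by intensity leaves the line between grades 2 and 3 undrawn. That is fair, and the fix allows for it.

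**Conclusion.** The point holds as an error in a stated rule. Grade 3 mixes severity with expectedness and with SAE criteria 2 to 4, although seriousness is to be decided separately. Followed as written, three of the four kinds of severe event short of life-threatening have no valid grade, and their recorded severity would be understated or blank. This includes severe forms of the named nicotine-excess signs when managed without admission.

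The conclusion rests on one assumption: that staff apply all the words of grade 3 as conditions. Staff who read only the word severe would grade sensibly, but against the text. The documents give no expected event rate, so the number of participants affected cannot be stated. SAE capture, HIC reporting and the planned analyses do not depend on the grade. The change should be made, but it is a correction to the safety record and not a flaw in the trial's safety oversight as a whole.

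**What to change.** Define grade 3 as an adverse event that is severe in intensity, whether or not it was anticipated and whether or not it led to admission. Remove the expectedness condition and the hospitalization, disability and birth-defect wording from the scale. Leave those outcomes to the SAE list and expectedness to the HIC reporting list, both already in item 12. A short intensity descriptor for each of grades 1 to 3 on the adverse event form would let assessors separate moderate from severe consistently.

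The cost is one line of the protocol and an edit to the form. The downside is that some events will appear as grade 3 that the current wording would list lower. SAE status and the 5-day report are unchanged.

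Separately, the sponsor should reconcile items 10 and 12 on whether a hospitalised nicotine event counts as anticipated. The grade 3 change does not settle that.
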